STUDY IDENTIFICATION

Project title Dopamine buffering capacity measured by phMRI as a novel biomarker of disease progression in PD

Short title Measuring Parkinson's Disease Progression

IRB Washington University Human Research Protection Office

IRB title Dopamine buffering capacity measured by phMRI as a novel biomarker of disease progression in PD

IRB ID # 201703122, first approved 16 May 2017

Grant support Michael J. Fox Foundation

Grant title Dopamine buffering capacity measured by phMRI as a novel biomarker of disease progression in PD

IND # 69,745, levodopa solution for intravenous use,
[name], sponsor-investigator (protocol # 009)

Protocol version (revision date) Version 20171024 (October 24, 2017)

OBJECTIVES

This application introduces a novel pharmacodynamic brain imaging method for objectively quantifying disease severity in Parkinson disease (PD). The method is levodopa pharmacological fMRI rapid quantitative pharmacodynamic imaging, or “bucket mapping” for short.

The novel method is based on the well-known clinical observation that the benefit from a dose of levodopa wears off more quickly as PD progresses. A well-known phenomenon in PD treatment is that early in the course of disease, a small dose of levodopa provides benefit for many hours. The body responds as if the levodopa in the plasma filled a reservoir and then slowly leaked out to produce benefit. With disease progression, even though the same amount of levodopa circulates in the blood, the benefit wears off much faster, as if the reservoir had become leakier. This wearing off of benefit has been quantified by a mathematical model that postulates a reservoir (central effect compartment) whose concentration of levodopa directly determines the clinical benefit. The buffering capacity in this model can be characterized by a single number, the effect site rate constant k_e . This constant, k_e , can be computed from serial measurements of plasma concentration and clinical status (like UPDRS scores or tapping speed). On average, patients with more severe disease and longer disease duration have a larger (“leakier”) k_e when modeled this way (Fig. 1) [1-6]. Dopamine buffering capacity as measured by k_e also correlates significantly with nigrostriatal denervation as measured by DOPA uptake (FDOPA PET) [7] or dopamine transporter imaging (FP-CIT SPECT) [8]. Unfortunately, clinical measurements are influenced by confounding factors such as patient fatigue and motivation. A direct, objective brain measure of response to LD may reduce this added variance.

The effect of levodopa in humans and other primates has been measured using regional cerebral blood flow (rCBF) to reflect regional brain activity [9-14]. Crucially, levodopa has *no* direct vascular effects when given with adequate carbidopa pretreatment (we use 200mg p.o. an hour before levodopa) [9-11].

Levodopa’s regional CBF effects mirror its regional effects on glucose metabolism (studied with 2DG autoradiography or FDG PET) and are prominent in pons and midbrain, thalamus, middle frontal gyrus, insula, putamen and cingulate cortex [10,12].

The expected rCBF response in midbrain to the rapid i.v. infusion, based on levodopa pharmacokinetics measured in PD [15] and published mean pharmacodynamic parameters [3,5], are quite distinct (Fig. 2), suggesting that even with some imperfection in the rCBF signal, we can reasonably expect to derive an

[figure not shown]

Figure 1. Across groups of PD patients, k_e is a surrogate for disease duration

[figure not shown]

Figure 2. Patients from different Hoehn and Yahr stages of PD are predicted to show different time courses of brain activity (unpublished data).

accurate k_e for a brain region that responds to exogenous levodopa with a dose-response curve anywhere close to that of clinical response. Midbrain, for instance, has a robust rCBF response to single, clinically sensible doses of levodopa [9-12,14].

This study's goal is to validate "bucket mapping" as an objective, quantitative measure of disease severity in PD. Success would position the new method for use as a surrogate endpoint in clinical studies of putative disease-modifying therapies for PD, potentially speeding up such trials dramatically.

Specific Aims

1. Test whether dopamine buffering capacity in midbrain and posterior putamen, measured by levodopa pHMRI, reflects clinical disease severity (disease duration, off-period motor function and clinical asymmetry) in 20 PD patients covering a range of current symptom severity and disease duration.
2. Test whether regional k_e values are affected by clinical treatment (6 weeks of clinically dosed carbidopa-levodopa (CD-LD) in 10 previously untreated PD patients).

Secondary Hypothesis

In Parkinson's disease (PD), while motor disturbances are the predominant and most readily recognized symptoms, various non-motor symptoms frequently co-occur. Cognitive functions such as working memory and executive control are on average worse in PD, although with substantial variability across patients. This variability highlights the need for ongoing studies exploring the nature of cognitive deficits in PD and their relationship to disease severity and progression. This study utilizes pHMRI-measured dopamine buffering capacity in putative motor regions as a model of motor disease severity. We propose extending this approach to include measures of cognitive performance utilizing [the NIH Toolbox](#) [22]. The NIH Toolbox cognitive measures were chosen because they can be completed relatively quickly (important to minimize patient discomfort when assessed in the medication off state), because it incorporates tasks that directly assess functions known to be impaired in PD, and because of its recognized validity [23]. The hypothesis is that the extent of DA buffering capacity loss in pertinent regions (such as the caudate nucleus) will explain a significant fraction of the variance in specific cognitive abilities.

Secondary Aim

3. Test whether dopamine buffering capacity in caudate reflects severity of cognitive dysfunction.

STUDY DESIGN

Overall study timeline

The study is planned for complete enrollment within 3 years.

Overview of each subject's participation

After thorough clinical assessment on a screening visit, subjects return on a separate day for levodopa pHMRI. Clinical severity ratings are repeated. Regional CBF data from pre-specified brain VOIs (volumes of interest) are collected continually with ASL fMRI before levodopa, during a 10-minute i.v. loading dose, and then repeatedly over the next approximately 90 minutes.

Levodopa-naïve patients in Aim 2 will have all scan day procedures repeated identically on a second scan day after 6 ± 1 weeks of clinically dosed treatment with CD-LD.

Screening visit

1. Potential subjects will review a written informed consent document with the investigator or designee and will have opportunity to resolve questions or concerns. All procedures below are performed only after written documentation of consent.
2. We will collect the following measures at screening:
 - a. Basic demographic information
 - b. MRI safety checklist
 - c. Handedness (Edinburgh Handedness Inventory)
 - d. PD symptom and treatment history including:
 - i. onset, laterality, dystonia, dyskinesia, psychosis
 - ii. past therapies (pharmacological, surgical and behavioral *e.g.* “Big and Loud”), their effects positive and negative, and current treatment
 - e. MMSE
 - f. Beck Depression Inventory
 - g. Michigan Alcoholism Screening Test
 - h. UPDRS Part II (past week activities of daily living)
 - i. NIH Toolbox cognitive measures (approx. 31 minutes—see table below)
3. [name] will review the history with the subject, perform a neurological and psychiatric examination, and document his review of the inclusion and exclusion criteria. For patients in Aim 2, [name] will discuss the risks and benefits of about 6 weeks of treatment with oral CD-LD and will document the clinical appropriateness.
4. Subjects who have not previously had an MRI of the head or neck will be exposed to a mock scanner.
5. Introduce subject to tapping speed measures and practice until comfortable

Cognitive measures from the NIH Toolbox			
Task - Cognitive Domain	Duration (minutes)	Screening Day (ON)	MRI Day (OFF)
Picture sequencing - Episodic memory	7	✓	
Flanker task - Inhibitory control and attention	3	✓	✓
List Sorting - Working memory	7	✓	✓
Picture vocabulary - Language	4	✓	
Oral reading recognition - Language	3	✓	
Dimensional change card sort - Executive function	4	✓	✓
Pattern comparison - Processing speed	3	✓	✓
Approximate total duration (minutes)	31	31	17

MRI scan day

1. Subjects will refrain from antiparkinsonian medications, oral protein intake, and caffeine after midnight the morning of the scan day.
2. Review of compliance with medication, food and caffeine restrictions
3. Notify PI of any substantive changes in health since the screening visit
4. Urine pregnancy test in any woman of child-bearing potential (*i.e.* not postmenopausal or surgically sterile)
5. Carbidopa 200mg p.o. (8 × 25mg Lodosyn® tablets or FDA-approved generic equivalent) at least 1 hour before levodopa infusion begins
6. Record vital signs
7. Tapping speed with each hand separately (60 seconds sequentially depressing two keys 20cm apart with audible and tactile feedback; record the lower score of the 2 counters)
8. Tapping speed with the more affected hand (60 seconds sequentially depressing two keys 2cm apart with the index finger) using a device equivalent to an MRI-compatible button device.
9. An i.v. line is placed in each upper extremity (preferably antecubital; alternatively a hand vein), one for infusing levodopa solution and one for repeated blood samples. Saline lock. Usually the more affected side (by “off” tapping speed) will be connected to the small-bore light-resistant tubing for the levodopa infusion, and a clear extension tubing will be connected to the less affected side for later blood samples.
10. “Practical off” UPDRS Part III (motor exam)
11. Visual analog scales (VAS) to rate current affective state, PD symptoms and side effects (nausea/vomiting, sleepiness, dizziness or lightheadedness, and overall feeling poorly or well)
12. NIH Toolbox cognitive measures (approx. 17 minutes—see table above)
13. Blood sample for [LD] (baseline levodopa concentration)
14. Enter MRI room
 - a. Headphones or ear plugs are worn to dampen the noise of the scanner and for communication between the experimenter and subject.
 - b. Padding behind the head, thermoplastic mask, and/or nylon tape are used to restrict head movement.
 - c. Structural MRI scans (3D TSE and MPRAGE) before or after the ASL scans, or at least one hour after the start of the levodopa infusion
15. During the phMRI scans:
 - a. Ensure that at least 50 minutes have passed since carbidopa dose before starting ASL
 - b. ASL before i.v. levodopa for 10 minutes, subject fixating a crosshair
 - c. ASL during i.v. levodopa loading dose, subject fixating a crosshair
 - d. ASL repeatedly during maintenance levodopa infusion, subject fixating a crosshair
 - e. Breaks during the maintenance phase—preferably at least 30 minutes after start of LD infusion—as needed for subject comfort
 - f. Tapping speed with the more affected hand is repeated in the scanner using an MRI-compatible button device once during the pre-levodopa scan block, once within 1 minute of the end of the loading dose, and again within 2 minutes of the following times measured from the start of the loading dose: 0:20, 0:30, and every 15 minutes thereafter.

- g. Blood samples within 1 minute of 0:05:00, 0:10:30, 0:12:00, and 0:15:00, within 2 minutes of 0:19 and 0:24, and within 3 minutes of 0:30, 0:45, 1:00, 1:30.

16. After the MRI session:

- a. tapping speed with each hand separately (60 seconds sequentially depressing two keys 20cm apart with audible and tactile feedback; record the lower score of the 2 counters)
- b. Tapping speed with the more affected hand (60 seconds sequentially depressing two keys 2cm apart with the index finger) using a device equivalent to an MRI-compatible button device.
- c. UPDRS part III
- d. Final blood sample
- e. Stop LD infusion
- f. VAS ratings
- g. Remove i.v. lines
- h. Record any benefit or side effect the patient noticed since the start of the infusion
- i. Provide a cab voucher if subject feels sleepy and had planned to drive home.

17. For Aim 2 subjects: Dispense supply of CD/LD tablets, confirm contact information, and confirm next study date.

Levodopa treatment between MR sessions (for subjects in Aim 2)

See “Treatments and Dosage,” a few pages below. This treatment is intended to match routine clinical practice. The initial treatment of PD varies among experts; CD/LD is a common option, and the most common one in the PI’s group practice, but other options include an MAO-A inhibitor, a dopamine agonist, or CD/LD combined with a COMT inhibitor. In other words, the 6-week initial treatment of Aim 2 subjects in this study is not off-label or experimental in the usual sense, but is standardized to a single treatment to reduce variability for the second pHMRI scan day.

With that exception, all procedures in this study are done for research purposes.

POTENTIAL RISKS

We have recently summarized the world literature on safety of i.v. levodopa and no SAEs are expected [16].

(The language below, in this section, is addressed to the patient, as in an informed consent document.)

You may experience one or more of the risks indicated below from being in this study. In addition to these, there may be other unknown risks, or risks that we did not anticipate, associated with being in this study. Some risks described in this consent document, if severe, may cause death. You will be told of any new information that may affect your willingness to participate in this study. [name] will answer any questions you have about these risks.

Levodopa

Likely:

- Temporary nausea
- Temporary sleepiness

Less likely:

- Temporary light-headedness (from lower blood pressure).
- Temporary vomiting
- Involuntary movements, hallucinations (seeing or hearing things that are not really there), delusions (being convinced of things that are objectively false), mental confusion, or impulse control disorders (like excessive gambling or change in sex drive). If any of these do occur, they are temporary.

Rare:

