Additional exclusion criteria for Aim 2 subjects:

- Taking levodopa currently or in the past month, or ever for more than a month
- Taking a dopamine agonist currently

CONCOMITANT MEDICATIONS

Required:

- none

Allowed:

- Most drugs that do not prominently affect the brain or constrict blood vessels
- Loratadine and other non-sedating antihistamines
- Benzodiazepines or “Z drugs” with short half-life used in the evening only
- Medications taken only as needed (less than daily), except those listed below

PROHIBITED MEDICATIONS

Daily use of any of the following medications:

- medications containing caffeine or theophylline
- benzodiazepines with long half-lives (e.g. clonazepam), except that a single dose at bedtime for treatment of REM sleep behavior disorder may be allowed at the discretion of the PI
- centrally-active antihistamines or anticholinergics (e.g. Benadryl®)
- orally administered nasal decongestants

If taken in the 24 hours prior to the MRI scans:

- p.r.n. benzodiazepines with long half-lives, p.r.n. Benadryl®, illicit drugs

If taken on the morning of the MRI scans:

- antiparkinsonian medications
- stimulants, nasal decongestants, caffeine, nicotine, alcohol

TREATMENTS AND DOSAGE

MRI Scan day

Treatments:

- Carbidopa (Lodosyn® 25mg tablets), or FDA-approved generic equivalent
- Levodopa 2mg/ml in normal saline, as described in previous IND communications, supplied by the Barnes-Jewish Hospital Research Pharmacy service

Dose:

Carbidopa: 200mg = 8 × 25mg tablets by mouth at least 1 hour before starting the levodopa infusion

Levodopa solution: based on age and body mass as follows:

Loading dose: 0.6426mg / kg / (10 min.)

Maintenance rate: 2.882 mg/kg/min. × 10⁻⁵ × (140 year – age)/year

This is the “final dose” in Table 1 [15]. The total levodopa dose for a 60-year-old 70kg subject over a 2.5-hour infusion is 68mg; an oral dose of 80 mg would provide the same total absorbed dose, though

over a slower time scale [17]. We have used this method with the 200mg carbidopa in previous studies and reported on its safety [13,18].

Oral treatment between scan days, in the Aim 2 group

Treatment:

- Carbidopa/levodopa 25/100mg tablets (Sinemet® or FDA-approved equivalent)

Dose:

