Secondary analyses will correlate k_e 's from secondary VOIs to all measures of disease severity (off tapping speed, off UPDRS III, disease duration) and to cognitive test scores (NIH Toolbox task scores adjusted for age), using the off-period scores for measures done on the scan day. Voxelwise analyses will use SPM with an initial threshold of $t \geq 3.0$ and statistical inference at the cluster level with a false discovery rate of 0.05. Another secondary analysis will use the k_e computed from the button box tapping speeds from the more affected hand and the levodopa concentrations, independent of the perfusion MRI data ("tapping k_e "). We will test whether the tapping k_e correlates with the k_e from the midbrain or contralateral posterior putamen, or other VOIs.

Note that we expect that k_e for some VOIs will correlate better than for other VOIs with measures of disease severity or duration. This conclusion is based on the expectation that a specific clinical effect may be better associated with dopamine buffering capacity in a specific (set of) brain region(s).

Therefore we expect that the k_e -vs-clinical slope may differ significantly from zero only for a subset of the VOIs; in other words, we do not expect the slopes to be parallel across VOIs, and therefore will not include all VOIs in a single ANCOVA with a factor for VOIs. However, any errors in estimating pharmacokinetic parameters (i.e., in reconstructing the continuous function $C_p(t)$, plasma levodopa concentration as a function of time for $t \geq 0$) occur at the subject level. Such errors will affect all k_e estimates for that subject (i.e., across all VOIs). Therefore we cannot assume independence across VOIs, within subject, for the measured estimates of k_e .

Visual analog scale (VAS) measures of side effects will be analyzed as repeated measures ANOVAs. Other variables (demographics, clinical measures, NIH Toolbox scores, etc.) will be summarized or compared as appropriate using standard statistical methods.

Additional analysis details

We will examine interactions of the key analyses with subject demographics or disease variables such as age or presence of dyskinesias.

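### Side-effect VAS is rated only before levodopa and after the infusion stops, so the planned ANOVA cannot grade side effects that arise and resolve in between

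*Combined protocol and SAP*

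**What the plan says.** All of this is in the combined protocol and SAP.

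- **First rating.** Study Design, MRI scan day, item 11: "Visual analog scales (VAS) to rate current affective state, PD symptoms and side effects". The side-effect items are nausea/vomiting, sleepiness, dizziness or lightheadedness, and a general item on feeling poorly or well. Item 11 precedes entry to the MRI room (item 14) and any levodopa.
- **During the infusion.** Item 15 covers the baseline, loading and maintenance scans. It lists ASL, timed blood samples and tapping ("Tapping speed with the more affected hand is repeated in the scanner using an MRI-compatible button device once during the pre-levodopa scan block", then at further set times). It lists no VAS.
- **Second rating.** Item 16, after the MRI session, lists repeat tapping, UPDRS part III, a final blood sample, then "Stop LD infusion" (16e), then VAS ratings (16f). Item 16f does not repeat the word current or describe the form.
- **Other record of side effects.** Item 16h: "Record any benefit or side effect the patient noticed since the start of the infusion". Item 16i provides a cab voucher for a subject who feels sleepy.
- **Analysis.** Analysis Plan, Data analysis: "Visual analog scale (VAS) measures of side effects will be analyzed as repeated measures ANOVAs". Nothing more is said about the VAS, and no specific analysis of the 16h record is described.
- **Expected effects.** Potential Risks, Levodopa, lists "Temporary nausea" and sleepiness as likely, and light-headedness and vomiting as less likely, each described as temporary.

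**The concern.** The VAS is the only graded side-effect measure with a named analysis. Its two ratings lie on either side of the infusion. A subject who feels sick during or soon after the loading dose and has recovered by the end of the session gives the same pair of current-state ratings as a subject who never felt sick.

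The other serial measures are followed through this period. Six of the ten timed blood samples fall within the first 24 minutes (nominal times 5, 10.5, 12, 15, 19 and 24 minutes), and tapping is repeated within a minute of the end of loading.

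What is at stake is limited: how completely the study can describe, on a graded scale, how the infusion was tolerated. Neither the primary comparisons nor the numbered aims use the VAS.

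**Working it through.** **1. Length of the infusion.** Treatments and Dosage gives a worked example: "The total levodopa dose for a 60-year-old 70kg subject over a 2.5-hour infusion is 68mg". The inputs from the same section are "Loading dose: 0.6426mg / kg / (10 min" minutes), and a maintenance rate of 2.882 × 10⁻⁵ × (140 − age) mg/kg/min.

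- Loading: 0.6426 × 70 = 44.98 mg.
- Maintenance rate at age 60: 2.882 × 10⁻⁵ × 80 × 70 = 0.1614 mg/min.
- If the 2.5 hours include the load: 0.1614 × 140 = 22.59 mg, total 44.98 + 22.59 = 67.58 mg (unrounded inputs), which rounds to the stated 68 mg.
- If 150 minutes of maintenance follow the load: 44.98 + 24.21 = 69.19 mg, which rounds to 69 mg.

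The stated figure is reproduced by the first reading, so the example is a 150-minute infusion including the load. The arithmetic is used here only to fix that duration.

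**2. Gap between the end of loading and the second VAS.**

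- Longer case, from the dosing example: 150 − 10 = 140 minutes.
- Shorter case, from the overview of each subject's participation (a 10-minute load, then about 90 minutes of imaging): a 100-minute infusion, so 100 − 10 = 90 minutes. This is a floor, because items 16a to 16d come after imaging and before the infusion is stopped.

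The gap is therefore about 90 to 140 minutes, assuming an infusion of 100 to 150 minutes. The unrated interval, counted from infusion start, is about 100 to 150 minutes.

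**3. What the ANOVA can use.** Write *b* for a subject's rating at item 11, *p* for the rating at 16f and *m* for the highest level reached in between. With two ratings on a scan day, the within-subject time effect depends only on *p* − *b*. The value *m* is never observed.

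| Course of the side effect | *p* − *b* | Graded by the ANOVA? |
|---|---|---|
| None | 0 | – |
| Arises and lasts to 16f | above 0 | Yes |
| Arises and resolves before 16f | 0 | No |

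For Aim 2 subjects, the second scan day repeats the same pair of ratings and adds none inside the infusion.

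**4. What item 16h adds.** Its window runs from infusion start, so it covers the third row of the table. The documents state no severity scale, timing or specific analysis for it.

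**The case against.** The strongest reply is that item 16h already covers the gap: staff ask about every side effect noticed from infusion start, and adverse events are reported under Safety Monitoring. That stands. A reader might infer that transient side effects go unrecorded, and the documents contradict this. What remains is that no grading or specific analysis of the 16h record is stated.

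A second reply is that the VAS directly follows an infusion still running until 16e, so effects sustained by maintenance would be rated, and item 16i anticipates sleepiness after the session. That also stands. The limitation concerns only effects that have resolved. Nor does temporary, in the risk text, mean over within the session, since the same patient-directed list also calls hallucinations and impulse control disorders temporary.

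A third reply is that rating during loading would compete with ASL under fixation and head restraint. That is fair, and the fix does not ask for it.

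Two stronger readings are tempting. The first is that the ANOVA is biased toward finding no side effects. A pre/post comparison is not biased for change in current state, and the plan does not say it will judge loading-dose tolerability from it. The second is that side effects must cluster around loading because most of the drug is given then. The split of the dose does not show when symptoms occur, and the documents give no symptom time course or duration.

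**Conclusion.** The point holds as a minor one. With the schedule as written, the planned VAS ANOVA describes change in current state from before levodopa to just after the infusion stops. It cannot grade side effects that arise during or after loading and resolve before item 16f, about 90 to 140 minutes after loading ends.

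This rests on three assumptions:

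- The infusion lasts 100 to 150 minutes.
- Item 16f uses the same current-state wording as item 11. This is a reasonable reading but is not stated, and the form is not in the documents.
- Part of the Potential Risks text, which was not available for this review, adds no further rating.

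How many subjects or how much severity would be missed cannot be estimated from the documents. The primary comparisons are unaffected.

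**What to change.** At item 16f, state that the existing marks rate current state. For nausea/vomiting, sleepiness, and dizziness or lightheadedness, add a second mark: *worst since the infusion began*.

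In Data analysis, keep the repeated measures ANOVA for current state. Add one sentence saying that the worst ratings will be reported descriptively (for example median, range and number above the subject's own baseline) together with the 16h reports.

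The cost is three extra marks on an existing form and one sentence in the plan, with no added visit, staff or scan time. The downside is that the worst rating relies on recall over about two hours and is a maximum over a period. It should therefore be described and not tested against the single baseline rating.

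### Minor participant-safety point: the scan-day cab voucher (item 16i) is triggered by sleepiness alone, although dizziness is a listed levodopa effect and is rated just before

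*Combined protocol and SAP*

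**What the plan says.** The relevant steps are in Study Design, MRI scan day, item 16 (after the MRI session). The UPDRS motor examination is repeated at 16c, the infusion is stopped at 16e, the visual analog scales are completed at 16f and the lines are removed at 16g. At 16h staff are told: "Record any benefit or side effect the patient noticed since the start of the infusion". Then comes 16i: "Provide a cab voucher if subject feels sleepy and had planned to drive home".

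The content of the scales is set at item 11 of the same list. Besides affective state, PD symptoms and nausea or vomiting, they cover "sleepiness, dizziness or lightheadedness, and overall feeling poorly or well".

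Potential Risks, under Levodopa, puts temporary nausea and temporary sleepiness in the likely group. The less likely group includes "Temporary light-headedness (from lower blood pressure" and, as a separate temporary entry, "Involuntary movements, hallucinations (seeing or hearing things that are not really there), delusions (being convinced of things that are objectively false), mental confusion".

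Safety Monitoring covers oversight by the principal investigator, adverse event reporting and a halt to enrolment after a related SAE. It does not deal with transport home.

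**The concern.** The plan already accepts that a levodopa effect bearing on driving should lead to the offer of a ride, but 16i writes this down for one effect. Light-headedness from a fall in blood pressure also bears on driving. The plan anticipates it, and the subject has just been asked about it. A subject who intended to drive, rates dizziness high and sleepiness low, and is handled strictly by the list would not be offered the voucher.

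What is at stake is the subject's safety on the way home and consistent handling between staff. Nothing scientific is at stake: k_e, the correlations in Aim 1, the before-and-after comparison in Aim 2 and the cognitive analyses do not depend on this step.

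**Working it through.** No figure in the plan needs reproducing, so the check is mainly a comparison of texts.

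**Symptom by symptom**

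| Effect named in Potential Risks | Group | Rated on the scales at 16f? | Other step where it could surface | Named in 16i? |
|---|---|---|---|---|
| Sleepiness | likely | yes | 16h | yes |
| Light-headedness | less likely | yes (dizziness or lightheadedness) | 16h | no |
| Mental confusion | less likely | not listed at item 11 | 16h, or noticed by staff | no |
| Involuntary movements | less likely | not listed at item 11 | 16h, or seen by staff at the 16c examination | no |

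The gap is clearest for light-headedness. It is a listed effect, it has its own rating at 16f, and that rating comes before the voucher decision. The case for confusion and involuntary movements is weaker, because they are not among the listed scale items. They depend on what the subject reports at 16h or on what staff see.

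**Order of steps.** 16c (examination), 16f (scales) and 16h (side effects) all precede 16i. A wider trigger can therefore use information already collected.

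**How often the step applies.** Sample Size gives 20 subjects for Aim 1 and 10 for Aim 2, with up to 2 in both. For Aim 2 the overview of participation says: "Levodopa-naïve patients in Aim 2 will have all scan day procedures repeated identically on a second scan day". So Aim 2 contributes two scan days per subject.

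- No overlap: 20 + 10 × 2 = 40 scan days.
- Overlap of 2: (20 − 2) + 10 × 2 = 38 scan days.

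Sample Size also says that more than two never-treated subjects may enter the Aim 1 analysis, which could lower this count if they replace other Aim 1 subjects. Make-up days after technical failures could raise it. The 38 to 40 is the number of occasions on which 16i is applied, not an estimate of affected subjects. The documents give no rate of dizziness without sleepiness, and no proportion of subjects who plan to drive.

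**The case against.** The strongest reply is that 16i is a courtesy step and not a fitness-to-drive criterion. It covers the likely effect that most plainly bears on driving and leaves less likely ones to staff judgement, which is a proportionate choice. The plan also states that this infusion method has been used before and its safety reported. That carries weight and is why the point is minor. It does not explain why a symptom rated minutes earlier should be left out of the written trigger, when including it costs almost nothing.

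Three stronger readings should be resisted.

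- A reader might infer that the plan gives no driving advice. The documents do not support that. In the text available for review, the levodopa risk list breaks off at its rare effects and the continuation was removed; a precaution could stand there. Such advice would still not widen the voucher trigger in 16i.
- A reader might infer that 16i clears every subject who is not sleepy to drive. It does not. It contains no word such as only, gives nobody permission to drive, and leaves staff free to arrange a ride for another reason.
- A reader might infer that confusion and involuntary movements are rated at 16f along with dizziness. Item 11 does not list them.

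**Conclusion.** The point holds as a small, cheap improvement to participant safety. Item 16i names one symptom. Light-headedness is a listed levodopa effect, is rated at 16f, and has no written link to the voucher. The number of subjects affected is unknown and probably small, and the step applies on 38 to 40 planned scan days. No aim, estimate or test is touched.

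The conclusion rests on two assumptions: that staff follow 16i as written, and that no removed text extends the voucher to other symptoms. If the removed text holds a driving precaution, the practical benefit shrinks, but the wording of 16i would still be worth aligning with it.

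**What to change.** Reword 16i along these lines: for any subject who intended to drive, offer a cab voucher if the subject is sleepy, dizzy or light-headed (16f, 16h), or if staff observe or the subject reports another effect that could impair driving, such as confusion or troublesome involuntary movements (16c, 16h). The investigator can set a rating threshold if one is wanted. Check the sentence against any driving instruction elsewhere in the risk or consent text so that the two agree.

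The cost is one sentence and a few more vouchers, at most one per scan day: 38 to 40 in total on the planned schedule, including those already due for sleepiness. No assessment is added and the study data are unaffected.
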